Other endpoints are individual visual symptom ratings included in the PRVSQ, rates of IOL repositioning procedures (secondary surgical intervention) due to IOL misalignment, rates of explants due to visual symptoms, distance visual acuities, mean percent reduction in absolute cylinder, mean refractive cylinder, mean refractive cylinder compared to the preoperatively-predicted cylinder, mean spherical equivalent, spherical equivalent compared to the preoperatively-predicted spherical equivalent, percent of eyes with cylinder and spherical equivalent (MRSE) within 0.50 D and within 1.00 D of the preoperatively-predicted spherical equivalent, rates of medical and/or lens findings, and rates of other adverse events. Preoperatively-predicted values will be based upon those generated from the TECNIS Symfony Toric IOL calculator.

DATA ANALYSIS:

The key time frame for analysis will be the 6-month visit. The first primary endpoint for this study will be the rate of bothersome visual symptoms,

The second primary endpoint will be the rate of those having a lot of difficulty with an activity due to halos, glare or starbursts as measured in the PRVSQ. The primary endpoint results will be compared between higher-cylinder toric IOL subjects and lower-cylinder toric control IOL subjects at the 6-month visit. The frequency, proportion and 95% Confidence Interval (CI) will be reported for higher-cylinder and lower-cylinder control subjects. This will be done for the higher-cylinder (ZXT300 and ZXT375) and lower-cylinder (ZXT150) groups.

Descriptive statistics will be used for reporting results. Visual acuity data will be reported by acuity line achieved. For questionnaire items, the frequency and proportion for each response will be reported. For refractive data, descriptive statistics will include mean, standard deviation, median, minimum and maximum and also the percent achieving absolute values within 0.50 D and 1.00 D of preoperatively-predicted values.

The frequency and proportion of primary and fellow eyes with adverse events or medical/lens findings will also be reported.

STUDY VISITS AND PROCEDURES:

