6. STUDY OBJECTIVES AND ENDPOINTS

The objective of this post-approval study is to evaluate the rate of bothersome visual symptoms

at 6 months for the Symfony Toric IOLs with approximately 2.0 D or more of cylinder correction at the corneal plane (Models ZXT300 and ZXT375) in a larger population in clinical practice compared to the control IOL (Symfony Toric Model ZXT150 IOL), and to ensure the continued safety of the approved devices.

Study endpoints will be evaluated at 6 months postoperatively.

6.1 **PRIMARY ENDPOINT:**

The primary co-endpoints are the rate of bothersome visual symptoms and the rate of difficulty with an activity due to the symptoms at 6 months postoperative.

The rate of difficulty with an activity due to the symptoms is determined by the percentage of subjects who respond "Yes" to the question "Is there anything you have a lot of difficulty with, or do not do, because of (visual symptom) at 6 months postoperative.

The frequency and proportion of subjects reporting one or more of these items

via PRVSQ questionnaire will be used to

determine the primary endpoint. This rate will be calculated for the higher-cylinder (ZXT300 and ZXT375) and lower-cylinder (ZXT150) groups.

6.2 OTHER ENDPOINTS:

- Other questionnaire responses, such as rates of degree of bother
- Rates of IOL repositioning procedures (secondary surgical intervention) due to IOL misalignment
- Rate of explants related to visual symptoms
- Rates of other adverse events
- Monocular uncorrected distance visual acuity
- Monocular best corrected distance visual acuity

- Mean percent reduction in absolute cylinder
- Mean refractive cylinder and mean refractive cylinder compared to preoperatively-predicted cylinder
- Mean spherical equivalent and mean spherical equivalent compared to preoperatively-predicted spherical equivalent
- Percent of eyes with absolute cylinder within 0.50 D and within 1.00 D of preoperatively-predicted cylinder
- Percent of eyes with spherical equivalent within 0.50 D and within 1.00 D of preoperatively-predicted spherical equivalent
- Rates of medical and/or lens findings

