- Approximately 1.00 D to 1.50 D resulting in a calculated lens power (using the web-based TECNIS Symfony Toric IOL Calculator) that requires implantation of a ZXT150 IOL in at least one eye for the subject to be eligible for the lower-cylinder group
- The eye with the higher toric power IOL will determine the model group
- The fellow eye must be the same or a lower toric power
- Predicted residual refractive cylinder based on the TECNIS Symfony Toric IOL calculator, taking surgically-induced astigmatism into account and using the posterior corneal astigmatism option, must be ≤0.50 D for all toric eyes
- Clear intraocular media other than cataract in each eye
- Availability, willingness, ability and sufficient cognitive awareness to comply with examination procedures and study visits
- Ability to understand, read and write English in order to consent to study participation and complete study questionnaires
- Signed informed consent and HIPAA authorization

8.2 EXCLUSION CRITERIA:

Note: All criteria apply to each eye

- Irregular corneal astigmatism
- Any clinically-significant corneal pathology/abnormality other than regular corneal astigmatism
- Previous corneal surgery
- Recent ocular trauma or intraocular surgery that is not resolved/stable or may affect visual outcomes
- Any clinically-significant pupil abnormalities (non-reactive, fixed pupils, or abnormally-shaped pupils)
- Subjects with conditions associated with increased risk of zonular rupture, including capsular or zonular abnormalities that may lead to IOL decentration, including pseudoexfoliation, trauma, or posterior capsule defects
- Known ocular disease or pathology that, in the opinion of the investigator, may affect visual acuity or require surgical intervention during the course of the study (macular degeneration, cystoid macular edema, diabetic retinopathy, uncontrolled glaucoma, etc.)
- Concurrent participation or participation during 30 days prior to preoperative visit in any other clinical study
- Planned monovision correction
- Patient is pregnant, plans to become pregnant, is lactating or has another condition associated with the fluctuation of hormones that could lead to refractive changes

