- Documentation of the TECNIS Symfony Toric IOL calculator choice of ZXT toric power for each eye and corresponding residual refractive cylinder and axis, as well as documentation of inclusion of the optional posterior corneal astigmatism algorithm

• PRVSQ Subject Questionnaire (Appendix B)

LENS POWER CALCULATIONS AND IOL SELECTION:

In order to verify subject eligibility and to optimize toric IOL selection and axis placement,

[figure not shown]
investigators will use the web-based TECNIS Symfony Toric IOL calculator (www.TecnisToricCalc.com) to determine the appropriate IOL model for each eye. Note that the TECNIS Symfony Toric IOL calculator provides toric IOL options based on predicted astigmatism, i.e., the vector sum of pre-existing corneal astigmatism and the expected effect of SIA. For this study, subjects are to have corneal astigmatism in at least one eye that, when taking SIA into account and using the PCA algorithm, has approximately 2.00 D to 3.00 D (higher-cylinder group) or 1.00 D to 1.50 D (lower-cylinder group) of corneal astigmatism to be corrected, and subjects must qualify for implantation of the suitable toric IOL by the TECNIS Symfony Toric IOL calculator.

Predicted residual refractive cylinder must be ≤ 0.50 D for all toric eyes. For all subjects, the IOL model selections chosen by the investigator via the TECNIS Symfony Toric IOL calculator are to be printed and maintained as source documentation.

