- Non-directed subject question responses at every visit.
- PRVSQ questionnaire: 1-month, 6-month and 1-year visits. Following completion of the questionnaire by the subject, the questionnaire is to be reviewed by the site personnel for reports of very or extremely bothersome visual symptoms of interest (halos, glare or starbursts) that impact daily living under overall conditions.
- Keratometry: 1-month, 6-month and 1-year visits
- Monocular uncorrected distance visual acuity at 4 m (Snellen or ETDRS): 1-month, 6-month and 1-year visits
- Manifest refraction (Snellen or ETDRS): 1-month, 6-month and 1-year visits; manifest refraction is to be performed using the Maximum Plus refraction method as detailed in **Appendix C**.
- Monocular best corrected distance visual acuity at 4 m (Snellen or ETDRS): 1-month, 6-month and 1-year visits
- Medical and lens findings from biomicroscopic slit-lamp exam: 1-month, 6-month and 1-year visits; findings of aqueous cells and flare, corneal edema, posterior capsule striae, posterior capsular opacification and IOL glistenings are to be rated using standardized grading scales provided in **Appendix D**.
- Ocular medications: In the event of a serious and/or device-related adverse event.
- Intraocular pressure: 1-month, 6-month and 1-year visits
- Fundus exam, if medically indicated
- Occurrence of Nd:YAG capsulotomy(ies)
- Occurrence of any adverse events

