21.3 ADDITIONAL ENDPOINTS

The frequency and proportion of subjects with each response will be reported for the individual visual symptom items for overall and with and without correction.

The frequency and proportion achieving each acuity level will be reported for monocular visual acuity.

[figure not shown]
Descriptive statistics will be reported for mean percent reduction in cylinder, refractive cylinder, cylinder vs preoperatively-predicted cylinder, spherical equivalent and spherical equivalent vs preoperatively-predicted spherical equivalent. The frequency and proportion of eyes within 0.50 D and within 1.00 D of the preoperatively-predicted values will be reported for refractive cylinder and spherical equivalent. Percent reduction in cylinder will be calculated for each eye using the following formula:

100*((Postop Ref. Cyl. - Preop K. Cyl.)/(Target Ref. Cyl. - Preop K. Cyl.)) Key: Ref. Cyl.=absolute refractive cylinder; K. Cyl.=keratometric cylinder;

[figure not shown]
Refractive data will be referred to the corneal plane prior to determining percent reduction in cylinder.

Enrollment data, demographic data, subject accountability data and operative complications/procedures will be reported using descriptive statistics. Visual symptom findings, adverse events and other key data will be reported at 1 year for subjects who experienced a repositioning procedure during the study or who were reported with bothersome visual symptoms at the 6-month visit.

The frequency and proportion of primary and fellow eyes with medical/lens findings will also be reported. In addition, rates of IOL repositioning procedures (secondary surgical intervention) due to IOL misalignment, rates of explants related to visual symptoms, rates of refractive procedures performed during the study period, and other adverse events will be reported.

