## 5.2 MANIFEST REFRACTION

Descriptive statistics of mean percent reduction in cylinder, refractive cylinder, cylinder vs preoperatively-predicted cylinder, spherical equivalent and spherical equivalent vs preoperatively-predicted spherical equivalent will be reported by IOL group. The frequency and proportion of eyes within 0.50 D and within 1.00 D of the preoperatively-predicted values will be reported for refractive cylinder and spherical equivalent. Percent reduction in cylinder will be calculated for each eye using the following formula:

100\*((Postop Ref. Cyl. - Preop K. Cyl.)/(Target Ref. Cyl. - Preop K. Cyl. )) Key: Ref. Cyl.=absolute refractive cylinder; K. Cyl.=keratometric cylinder;

Refractive data will be referred to the corneal plane prior to determining percent reduction in cylinder.

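### Agreement of achieved with predicted cylinder is judged by magnitude alone, so as a measure of prediction accuracy the 0.50 D and 1.00 D rates can only equal or exceed the vector-based rates

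*Protocol*

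**What the plan says.** Protocol 6.2 names the endpoint as "Percent of eyes with absolute cylinder within 0.50 D and within 1.00 D of preoperatively-predicted cylinder". The synopsis describes the refractive summaries as including "the percent achieving absolute values within 0.50 D and 1.00 D of preoperatively-predicted values". SAP 5.2 repeats the rule: the proportion of "eyes within 0.50 D and within 1.00 D of the preoperatively-predicted values will be reported for refractive cylinder". The key to the percent-reduction formula, the same in Protocol 21.3 and SAP 5.2, reads "Key: Ref. Cyl.=absolute refractive cylinder; K. Cyl.=keratometric cylinder". No readable section plans a vector comparison or a comparison of achieved with predicted axis.

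The ingredients of a vector comparison are nevertheless called for. Protocol 11.3 describes the calculator's prediction as a vector sum of corneal and surgically-induced astigmatism, and asks sites to document the chosen toric power with the "corresponding residual refractive cylinder and axis". Under Protocol 11.6, "manifest refraction is to be performed using the Maximum Plus refraction method" at 1 month, 6 months and 1 year.

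The predicted residual is capped by eligibility (Protocol 8.1): it "must be ≤0.50 D for all toric eyes". The endpoint is descriptive, with no test, margin or success criterion.

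**The concern.** Cylinder has a size and a direction. The plan makes a prediction with both, then scores the result on size alone. An eye predicted to have 0.50 D at axis 90 that ends with 0.50 D at axis 180 has missed its prediction by 1.00 D, but scores an error of zero and counts as accurate.

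At stake is what the agreement rates mean. Readers of a toric lens report will tend to take them as showing how well the calculator and surgery delivered the planned refraction. On that reading they are too favourable, and possibly more so for the higher-power lenses that the study compares with ZXT150.

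**Working it through.** The documents give no expected rate or power for this endpoint, so there is no figure of the plan's own to reproduce.

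**Inputs from the documents.** Lens cylinder at the corneal plane, C: 1.03 D (ZXT150), 2.06 D (ZXT300), 2.57 D (ZXT375), from Protocol Table 1. Predicted residual at most 0.50 D, from Protocol 8.1. Cut-offs 0.50 D and 1.00 D.

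**Inputs assumed.** The distributions of predicted residual and of prediction error, stated at each step below.

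**1. Direction.** Let a be the achieved cylinder, b the predicted cylinder and δ the axis difference.
- Magnitude error: |a − b|.
- Vector error: sqrt(a² + b² − 2ab·cos 2δ).

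Since cos 2δ ≤ 1, the vector error is never smaller than |a − b|. Every eye that passes the vector rule passes the magnitude rule, so the magnitude rate is always at or above the vector rate.

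**2. Worked eyes.**

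| Predicted | Achieved | Magnitude error | Vector error |
|---|---|---|---|
| 0.50 D at 90 | 0.50 D at 180 | 0.00 D | 1.00 D |
| 0.50 D at 90 | 0.50 D at 135 | 0.00 D | 0.71 D |
| 0.50 D at 90 | 1.00 D at 180 | 0.50 D | 1.50 D |
| 0.25 D at 90 | 0.25 D at 180 | 0.00 D | 0.50 D |

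The vector error passes 0.50 D when δ exceeds ½·acos[(a² + b² − 0.25)/(2ab)]. This is 30.0 degrees for 0.50 D and 0.50 D, and 37.8 degrees for 0.25 D and 0.50 D.

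The effect is bounded. When a = b the vector error is 2b·sin δ, at most 2b. An eye with exactly the predicted amount is therefore misclassified at 0.50 D only if b exceeds 0.25 D. With b capped at 0.50 D, it is never misclassified at 1.00 D.

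**3. Size under general prediction error.** Assumed: predicted residual uniform on 0 to 0.50 D at a random axis; normal error with SD s on each double-angle component. The vector rate is 1 − exp(−d²/2s²) at cut-off d; at d = 0.50 D and s = 0.3 that is 1 − exp(−0.125/0.09) = 75.1%. The magnitude rate comes from simulation of 1,000,000 eyes per scenario.

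| s (D) | 0.50 D: magnitude / vector | Gap (points) | 1.00 D gap (points) |
|---|---|---|---|
| 0.2 | 98.6% / 95.6% | 3.0 | 0.0 |
| 0.3 | 88.5% / 75.1% | 13.4 | 0.3 |
| 0.4 | 74.2% / 54.2% | 19.9 | 2.5 |
| 0.5 | 60.8% / 39.4% | 21.4 | 6.5 |

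Over the same range of s, the 0.50 D gap is 2.6 to 12.2 points if every predicted residual is 0.10 D, and 3.5 to 33.7 points if every one is 0.50 D.

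**4. Size under rotation alone.** Rotation by t gives a vector error of 2C·sin t, which reaches 0.50 D at about 14 degrees (ZXT150), 7.0 degrees (ZXT300) and 5.6 degrees (ZXT375). Assumed: normal rotation with the same SD for every model, predicted residual as in step 3, no other error.

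| Lens | SD 5°: magnitude / vector | Gap | SD 8°: magnitude / vector | Gap |
|---|---|---|---|---|
| ZXT150 | 99.9% / 99.5% | 0.4 | 96.8% / 92.1% | 4.7 |
| ZXT300 | 92.1% / 83.6% | 8.5 | 75.9% / 61.5% | 14.4 |
| ZXT375 | 85.5% / 73.6% | 11.9 | 66.3% / 51.5% | 14.8 |

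At SD 5 degrees, ZXT150 leads ZXT300 by 99.9 − 92.1 = 7.8 points on the magnitude rule and 99.5 − 83.6 = 15.9 on the vector rule. Against ZXT375 the leads are 14.4 and 25.9. Placing the predicted residual along the lens axis instead of at random gives gaps of 0.4, 10.2 and 13.6 points.

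**The case against.** A reader might infer that the endpoint cannot see axis error. The documents do not support that, because the axis of the residual refraction is not the axis of the lens. For a lens planned on the steep meridian with signed predicted residual r, rotation by t gives an achieved residual whose square is r² + 4C(C + r)·sin² t. With C at least 1.03 D and |r| at most 0.50 D, rotation alone always raises the magnitude. An eye with the predicted amount at the wrong axis therefore cannot come from rotation alone; the right-angle example is an under- or overcorrection flip. Even at |r| = 0.50 D the magnitude rule fails the eye beyond about 11 to 14 degrees for ZXT300 and 9 to 11 for ZXT375. This stands: the rule is less sensitive to misalignment, not blind to it.

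A reader might also take the thresholds in step 2 to mean that only 30.0/90 = 33% or 37.8/90 = 42% of such eyes are truly accurate. That needs axis differences spread evenly over all angles, an extreme case and not an expected rate.

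Third, Protocol 6.2 says absolute cylinder, and as a statement of magnitude the rate is right. That stands too, so this is a matter of what the rate can be used for. The plan also reports repositioning for misalignment, uncorrected acuity and mean refractive cylinder. These pick up some consequences of misalignment, but none measures prediction error, and repositioning counts only eyes returned to surgery.

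**Conclusion.** The point holds as a limit on interpretation. The direction is certain: read as prediction accuracy, the magnitude rates equal or exceed the vector rates. The size cannot be derived from the documents. Under the assumptions shown it is about 3 to 21 points at 0.50 D and 0 to 6.5 points at 1.00 D. Under rotation alone with SD 5 degrees it is about 0.4, 8 and 12 points for ZXT150, ZXT300 and ZXT375. The magnitude rule is then more favourable to the higher-cylinder lenses and narrows their difference from the control, provided rotation is similarly distributed across models.

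It would go too far to call the planned rate wrong, or to carry the point over to the study's conclusions. This is a descriptive other endpoint; the primary endpoints, both questionnaire-based, and the sample size are unaffected. The improvement is worthwhile but minor.

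**What to change.** In Protocol 6.2 and 21.3 and SAP 5.2, define prediction error as the double-angle vector difference sqrt(a² + b² − 2ab·cos 2δ) between achieved and predicted residual cylinder, with both referred to the corneal plane. Report by group, for primary and fellow eyes, the percent of eyes whose vector difference is at most 0.50 D and at most 1.00 D, and use these as the measure of prediction accuracy. Keep the existing rates, labelled as magnitude only.

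The programming is a few lines. The other costs are a minor protocol and SAP amendment (Protocol 13 requires FDA and IRB approval of modifications before they are implemented) and a check of the database. Protocol 11.3 has the calculator selections printed and kept as source documentation, but no readable section shows the predicted axis as a database field. Confirm that it and the postoperative refraction axis are entered. The accuracy rate reported will probably be less favourable.

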7. STUDY PRODUCTS

7.1 INTRAOCULAR LENSES

TECNIS Symfony IOLs, both toric and non-toric, are posterior-chamber, 1-piece, aspheric, hydrophobic acrylic foldable IOLs and are to be implanted in the capsular bag following cataract extraction. The Symfony IOLs have a spherical posterior optic with a diffractive surface to provide an extended depth of focus and an anterior aspheric optic; the Symfony Toric IOLs also have a toric surface to correct for ocular astigmatism.

The TECNIS Symfony Toric Model Series ZXT IOLs included in this study are intended for cataract patients with pre-existing corneal astigmatism that, when taking surgically-induced astigmatism into account and using the TECNIS Symfony Toric Calculator's PCA algorithm, have approximately 2.00 D to 3.00 D (higher-cylinder group) or 0.75 D - 1.50 D (lower-cylinder group) of predicted corneal astigmatism to be corrected (**Table 1**).

ZXT IOL	Cylinder Power (D)		Correction Range Based on	
Model	IOL Plane	Corneal Plane	Combined Corneal Astigmatism (Preoperative Kcyl ^a + SIA ^b)	
ZXT150	1.50	1.03	0.75 – 1.50 D	
ZXT225	2.25	1.55	1.50 – 2.00 D	
ZXT300	3.00	2.06	2.00 – 2.50 D	
ZXT375	3.75	2.57	2.50 – 3.00 D	

TABLE 1 Symfony Toric IOL Astigmatism Correction Range

^a Keratometric cylinder

^b Surgically-induced astigmatism

[°] Model ZXT225 eyes may be included in the study; however, the fellow eye must require either a ZXT300 or ZXT375 IOL. Model ZXT225 is not the subject of this study.

The Model ZXT IOLs have two sets of four axis orientation marks 180° apart in the outer periphery of the anterior optic surface (**Figure 1**) to indicate the meridian of the lowest power (flat meridian). These axis orientation marks are for proper alignment of the flat meridian of the IOL with the steep meridian of the corneal curvature.

[figure not shown]

FIGURE 1: Drawing and Photograph of a Model Series ZXT IOL

INDICATION

The TECNIS Symfony Toric Extended Range of Vision IOLs, including Models ZXT150, ZXT225, ZXT300, and ZXT375, are indicated for primary implantation for the visual correction of aphakia and for reduction of residual refractive astigmatism in adult patients with greater than or equal to 1 diopter of preoperative corneal astigmatism, in whom a cataractous lens has been removed. The lens mitigates the effects of presbyopia by providing an extended depth of focus. Compared to an aspheric monofocal IOL, the lens provides improved intermediate and near visual acuity, while maintaining comparable distance visual acuity. The Model Series ZXT IOLs are intended for capsular bag placement only. Note that Model ZXT225 may be included in the study; however, the fellow eye must require either a Model ZXT300 or ZXT375 IOL. Model ZXT225 is not the subject of this study.

The TECNIS Symfony Extended Range of Vision IOL, Model ZXR00, is indicated for primary implantation for the visual correction of aphakia in adult patients with less than 1 diopter of pre-existing corneal astigmatism, in whom a cataractous lens has been removed. The lens mitigates the effects of presbyopia by providing an extended depth of focus. Compared to an aspheric monofocal IOL, the lens provides improved intermediate and near visual acuity while maintaining comparable distance visual acuity. The Model ZXR00 IOL is intended for capsular bag placement only. Note that Model ZXR00 will only be implanted in fellow eyes for this study.

STORAGE AND DISTRIBUTION

All lenses will be obtained from the site's own inventory. All study lenses should be stored in the original packaging and kept in a dry place. Lenses should not be stored in direct sunlight or at temperatures greater than 45° C (113°F). Each lens is packaged in a lens tray and sealed in a peel-pouch. The lens is sterile as long as the package has not been opened or damaged and the shelf-life expiration date has not been exceeded.

Table 2 lists the general design characteristics of the Symfony Toric IOLs:

CHARACTERISTICS	Symfony Toric IOL Model Series ZXT
Lens Design	1-piece foldable posterior-chamber lenses with a toric-aspheric anterior surface, a diffractive design on the posterior surface, and a maximum and a minimum radii of curvature perpendicular to each other
Lens Model	Surface-treated SENSAR [®] soft acrylic (hydrophobic acrylic with a covalently-bound UV absorber)
DIMENSIONAL FEATU	RES
Overall Diameter	13.0 mm
Optical Center Thickness	0.7 mm (20.0 D Lens)
Haptic Angle	No angulation, but offset from the optic body
Optic Body Diameter	6.0 mm
Haptic Material	Same as optic
Haptic Width	0.39 mm
Haptic Thickness	0.46 mm
Haptic Style	TRI-FIX Design Modified C, integral with optic
Other Features	Axis orientation marks
OPTICAL FEATURES	
Optic Shape	Biconvex
Anterior Optic Profile	Toric aspheric with a maximum and a minimum radii of curvature perpendicular to each other
Posterior Optic Profile	Spherical
Optic Edge Design	PROTEC™ squared posterior edge
Dioptric Power Range	+5.0 to +34.0 D in 0.50 D increments
Cylinder Power Range	1.50 D, 2.25 D ^b , 3.00 D and 3.75 D (at the IOL plane)
Refractive Index	1.47 (at 35° C)
Theoretical A-constant ^a	118.8 for ultrasound biometry
	119.3 for optical biometry

 TABLE 2

 Lens Characteristics of the Symfony Toric Model ZXT

^a For lens power calculations, the investigator's personalized A-Constant or Surgeon Factor for the TECNIS Symfony Model ZXR00 IOL or TECNIS Symfony Toric Model ZXT IOLs is to be used.

[figure not shown]
